6.0 RECIPIENT PRE-TREATMENT EVALUATION

1. Medical history, physical examination, vital signs, height and weight.
2. Karnofsky Performance Status.
3. CBC with differential and platelet count, serum creatinine, bilirubin, alkaline phosphatase, ALT, and AST.
4. CMV antibody test, hepatitis panel (HepA Ab, HepB Sab, HepB Sag, HepB Core Ab, HepC Ab), herpes simplex, syphilis, HIV and HTLV 1 antibody, and varicella zoster virus.
5. High resolution HLA typing, if not already performed.
6. Bone marrow aspirates for pathology and cytogenetics and/or biopsy, for patients with <10% circulating peripheral blasts.
7. CMV PCR, EBV PCR
8. HLA antibodies
9. Assessment of disease status (bone marrow, cytogenetics, molecular testing etc..) within 30 days prior to start of chemotherapy.
10. CRP, ESR (erythrocyte sedimentation rate), procalcitonin
11. Serum cytokine levels (IL1, IL6, TNF, TNFR1, REG3 alpha, ST2) (Samples to be drawn and stored for later analysis)

7.0 REQUIRED DATA

7.1 Pre-Study Testing Intervals

To be completed within 30 DAYS before infusion of stem cells:

- All bloodwork
- History and physical
- bone marrow

All others to be completed within 42 DAYS before infusion of stem cells:

Tests & Observations on patient	Prior to infusion of stem cells	Day 0-Day 60	Beyond day 60 (only if evidence of donor chimerism)
Informed Consent	X		
History and Progress Notes	X	A ☺	E
Physical Examination	X	A ☺	E
Height	X		
Weight/Body Surface Area	X		
Karnofsky Performance Status	X		E
Drug Toxicity Assessment		B	
GVHD/Engraftment Syndrome assessment		B	E
Laboratory Studies			
CBC, Differential, Platelets	X	A	E
Serum Chemistry **	X	B	E
Uric Acid	X		E
Magnesium	X		E
PT (INR), PTT, Fibrinogen	X		
Urinalysis	X		
EBV PCR	X	B	E
CMV PCR	X	B	
Lymphocyte subsets (laboratory tests 17603138 and 17603144)	X	D	E
Chimerism Peripheral Blood	X	C	E
ESR, CRP, procalcitonin	X	D	E
HLA antibodies	X		F
CMV antibody test, hepatitis panel (HepA Ab, HepB Sab, HepB Sag, HepB Core Ab, HepC Ab), herpes simplex, syphilis, HIV and HTLV 1 antibody, and varicella zoster virus	X		
Chest x-ray or Chest CT	X		
Staging			
Bone Marrow Asp,biopsy with cytogenetic and Flow and chimerism†	X***	Before day 60	
Correlative Laboratory studies			
Microchimerism*		C	E
Serum Cytokine level ((IL1, IL6, TNF, TNFR1, REG3 alpha,	X*	D*	E*

Tests & Observations on patient	Prior to infusion of stem cells	Day 0-Day 60	Beyond day 60 (only if evidence of donor chimerism)
ST2) (sample stored for subsequent analysis)			

† A bone marrow biopsy is required for response assessment in the event of a dry tap or an aspiration that is inadequate for interpretation.

A: At least twice weekly.

B: At least weekly starting on day of infusion

C: Weekly until day 60. Every two months thereafter until one year after cell infusion.

D: Every two weeks until Day 60. Lymphocyte subsets are performed only at Day 28.

E: At least monthly until Day 180 and at least every two months thereafter until one year. Lymphocyte subsets are performed only at Day 100, Day 180, and 1 year.

F: Performed only at Day 100 • Physical exam and history will focus on signs and symptoms of GVHD

*microchimerism assays will be performed in selected cases of CBU infusion and based on HLA type of recipient, CBU unit and Mother of the CBU donor.

**Serum chemistry to include BUN, creatinine, electrolytes, alanine aminotransferase, aspartate aminotransferase, alkaline phosphatase, total bilirubin, calcium, glucose, total protein, and albumin.

***Not required for subjects with $\geq 10\%$ circulating peripheral blasts observed on manual differential.

7.2 CBU Graft Evaluation and Preparation Prior to Infusion:

Upon thawing and prior to infusion, CBU will be evaluated by

- Viability testing (including 7AAD, CFU)
- Cell Subset determination including at least CD3, CD34 –consider CD19, CD4, CD8
- CBUs will be washed prior to infusion.
- Sample for microchimerism (selected cases, based on maternal and fetal HLA type)

7.3 Haplo Donor and Product Evaluation Prior to Infusion.

Haplo donor evaluation will follow the routine transplant program policies. This will include screening for COVID (PCR test) as stipulated in Transplant Policies.

Haplo product may be infused fresh, after washing, or using bedside thaw.

The haplo product will be evaluated:

- At the time of collection using:
 - Cell subset determination including at least CD3, CD34, consider CD19, CD4, CD8
 - Viability testing including Trypan Blue.
- At the time of cell infusion using
 - Viability testing (including 7AAD, CFU)

- Cell subset determination including at least CD3, CD34.

7.4 Response Assessment

A bone marrow examination to document response must be performed in all patients on or before Day 60. Physicians should consider earlier bone marrow exams in patients whose peripheral blood counts are not recovering or recovering sluggishly. Subsequent treatment (consolidation, salvage therapy, etc) will be at the discretion of the treating physician.

Patients will continue to be followed for survival, and disease status. Samples for correlative studies will be collected, if possible at 2 month intervals after day 60, until one year after treatment.

8.0 ADVERSE EVENT REPORTING REQUIREMENTS

Adverse event (AE) monitoring and reporting is a routine part of every clinical trial. The investigator will be required to provide appropriate information concerning any findings that suggest significant hazards, contraindications, side effects, or precautions pertinent to the safe use of the drug under investigation. Safety will be monitored by evaluation of adverse events reported by subjects or observed by investigators or research staff, as well as by other investigations such as clinical laboratory tests, x-rays, and electrocardiographs.

8.1 Investigational Risks

The investigational component of the study is the infusion of allogeneic cells. The possible complication of such treatment would be the development of severe GVHD and/or prolonged myelosuppression. The chemotherapy preceding adoptive cell therapy has numerous side effects and possible complications, but these are not considered investigational risks since the chemo is standard of care.

8.2 Adverse Event Characteristics

- **CTCAE term (AE description) and grade:** The descriptions and grading scales found in the revised NCI Common Terminology Criteria for Adverse Events (CTCAE) version 4.0 will be utilized for AE reporting. A copy of the CTCAE version 4.0 can be downloaded from the CTEP web site (<http://ctep.cancer.gov>).
- **Attribution** of the AE:
 - Definite – The AE is *clearly related* to the study treatment
 - Probable – The AE is *likely related* to the study treatment
 - Possible – The AE *may be related* to the study treatment
 - Unlikely – The AE is *doubtfully related* to the study treatment

- Unrelated – The AE is *clearly NOT related* to the study treatment

8.3 Recording and Reporting of Adverse Events and SAEs

- Safety reporting will be 21 CFR 312.32 compliant.
- Salvage chemotherapy for AML/MDS is a complex procedure with the possibility of prolonged initial admission and numerous immediate and delayed complications as well as frequent readmissions.
- **Expected toxicities are those listed in the consent form and include regimen-related toxicities, myelosuppression, opportunistic infections, haplo-immunostorm, engraftment syndrome and GVHD. These will be captured in the transplant database and reported to the IRB on a quarterly basis**
- **Unexpected** adverse events are those leading to ICU admission or to death. Such toxicities will be reported immediately to the designated study chairman. Such events will be reported to the local IRB within the institution's prescribed time period.

	Immediate Reporting	Report quarterly
Hematopoietic Toxicity	Death	Time to Hematopoietic recovery
Extramedullary Toxicity	Fatal toxicity and toxicity requiring ICU admission	Grade III-IV toxicities not requiring ICU admission
Infections	Fatal or requiring ICU admission	Grade II-IV
Acute GVHD	Fatal or Grade IV	Grade II-IV
Chronic GVHD	Fatal or requiring ICU admission	Limited and extensive
Haplo-immunostorm and/or engraftment syndrome	Fatal or requiring ICU admission	All others.

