10.2 Stopping Rules

The occurrence of adverse events that are life-threatening, lead to ICU admission or death (as defined in section 8.3) will lead to temporary suspension of enrollment and immediate assessment of events.

The study will also be paused if there is death that is directly attributed to infusion of adoptive cell therapy; for example severe infusion related reaction, infection from contaminated unit, Grade 5 GVHD etc.

Enrollment may resume upon assessment by the investigators that there are no safety issues and upon appropriate revision of the protocol – if required.

After 10 patients are enrolled in each group, the incidence of the above-defined life-threatening complications will be assessed. If more than one patient out of 10 enrolled patients (i.e., $>10\%$) in a cohort experiences either of these complications, the cohort will be stopped for safety. Each cohort will be evaluated separately with respect to these complications. Additionally, if three or more of the first five patients in a particular cohort experiences either of these complications, the cohort will also be stopped. This is illustrated in the Table below.

N treated subjects	5	10	15	20
No with gr III-IV GVHD to trigger stopping rules	2	2	3	4
No with prolonged myelosuppression to trigger stopping rules	2	2	3	4
No with either Gr III-IV GVHD or with prolonged myelosuppression to trigger stopping rules	3			

For assessment of secondary objectives, descriptive statistics will be utilized via the method of binary proportions and 95% confidence intervals will be calculated to assess the precision of the obtained estimates. All analyses will be performed in SAS Version 9.3 (SAS Institute, Inc., Cary, NC) and Stata Version 13.0 (StataCorp, College Station, TX).

Addendum 5/26/2020: To date stopping rules have not been met in the CBU cohort after enrolling more than 30 patients. The Haplo cohort has not accrued.

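### Section 8.3 defines expected toxicities by listing but unexpected events by outcome, so a serious, unlisted, possibly cell-related event managed outside the ICU has no prompt event-level reporting route

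*Combined protocol and SAP*

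**What the plan says.** Section 8.3 sorts adverse events under two labels. The first goes by listing: "Expected toxicities are those listed in the consent form and include regimen-related toxicities, myelosuppression, opportunistic infections", with haplo-immunostorm, engraftment syndrome and GVHD completing the examples. These go to the IRB quarterly. The second goes by outcome: unexpected "adverse events are those leading to ICU admission or to death". These go at once to the study chairman, and to the IRB within the institution's time limit.

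The table in 8.3 then assigns event types to an immediate or a quarterly column. For extramedullary toxicity the immediate entry is "Fatal toxicity and toxicity requiring ICU admission" and the quarterly entry is "Grade III-IV toxicities not requiring ICU admission". For infections, fatal or ICU cases are immediate and grades II-IV are quarterly. Acute GVHD is the only row with an immediate trigger by grade ("Fatal or Grade IV"). The same section opens with "Safety reporting will be 21 CFR 312.32 compliant".

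Section 10.2 provides for temporary suspension of enrollment: "The occurrence of adverse events that are life-threatening, lead to ICU admission or death (as defined in section 8.3"). Section 13 sends all adverse events to the DSMB after each set of five patients accrued to an arm. Section 8.2 records CTCAE term, grade and a five-level attribution for each event.

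**The concern.** Whether an event is new and how severe its outcome is are separate questions. Section 8.3 answers the first with the second, so the unexpected label carries no information about novelty. A known chemotherapy complication that leads to the ICU is labelled unexpected, although section 10 itself describes reinduction as extremely toxic. A new toxicity of the cell product that is handled on the ward is not.

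Safety is the primary objective (1.1), detecting toxicity is called a major goal (2.5), and the cell infusion is the investigational component (8.1). There is no control group, so prompt notice of a new, related, serious event is an important protection for the next patient. It matters still: the May 2020 addenda raise the CBU cohort to 60 treated patients and report that the haplo cohort has not accrued. Any first haplo patients would be infused under these reporting rules.

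**Working it through.** The plan gives no figure on this point, so the check is a trace through the rules. Take an event that is serious, not listed in the consent form, at least possibly related to the cells, managed outside the ICU and not fatal.

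1. **Expected under 8.3?** No, because it is not listed.
2. **Unexpected under 8.3?** No, because there is no ICU admission and no death. The event is in neither class. Conversely, a listed infection that needs the ICU is in both.
3. **Table in 8.3.** An extramedullary event of grade III-IV goes to the quarterly column, and so does an infection of grade II-IV. Neither row asks whether the event is listed or related. Outside acute GVHD, every immediate entry is death, or death and ICU admission.
4. **Attribution in 8.2.** It is recorded, but no rule in 8.3 uses it.
5. **The 312.32 sentence.** It applies in general terms. The section gives no route, time limit or listing test to put it into effect, and does not say whether it overrides the table.
6. **DSMB (section 13).** Timing follows accrual, not the event. If the event occurs in the first patient of a set, the report waits for 5 − 1 = 4 more patients in that arm. If it arises after a set has been reported, it waits for the next 5.
7. **Suspension rule (10.2).** If the event is life-threatening, the wording reaches it. However, 8.3, to which the rule points, defines only the ICU and death limbs. The opening of section 10 does limit the life-threatening complications it counts, to grade III-IV GVHD and unexplained prolonged myelosuppression, but the cross-reference does not lead there. If the event is serious but not life-threatening, the rule does not reach it.
8. **Numerical stopping boundaries (10.2).** They count only those two complications, so a new toxicity of another kind is never counted.

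The longest wait on the quarterly route is one quarter, 12 / 4 = 3 months. That is a maximum, and the actual wait depends on when in the quarter the event occurs.

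**The case against.** The best defence is that the event would not go unseen. Section 7.1 requires toxicity and GVHD assessment at least weekly to day 60, section 12 has the investigators review inpatients weekly, section 13 gives the DSMB all adverse events, and the 312.32 sentence can be read as governing whatever the table omits. The overlap between the two labels also does little harm, because the table sends fatal and ICU cases to the immediate column. Much of this stands. The study team would normally know of the event; what is delayed is formal notice outside the team. But none of these provisions sets a prompt reporting route triggered by such an event.

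A reader might also infer more than the documents support:

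- **That such an event is reported only quarterly.** The DSMB report and the general compliance sentence also apply.
- **That it never reaches the suspension rule.** Life-threatening is a separate limb of 10.2, so the gap is confined to serious events that are not life-threatening, plus an undefined term.
- **That 10.2 proves there are unlisted hazards.** Its examples ("severe infusion related reaction, infection from contaminated unit") illustrate deaths attributed to the infusion, which are already immediate. The consent form is not available for review and may list them.
- **That the plan breaches the regulation.** The documents do not reproduce the regulation. They show only a general statement and a specific table left unreconciled.
- **That a given number of further patients would be infused in the meantime, perhaps with product from the same source.** No accrual rate is stated. Cord units are selected for each patient, and haplo donors are the patient's own relatives.

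**Conclusion.** The point holds as a defect in the stated rules. Section 8.3 uses two different criteria for expected and unexpected, and its table places a serious, unlisted, possibly cell-related event managed outside the ICU in the quarterly column. The size is a delay in formal notice of up to one quarter to the IRB, and until the next five-patient report to the DSMB. The 10.2 cross-reference is a second, smaller fault, since it relies on 8.3 for a term that 8.3 does not define.

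The conclusion assumes that staff follow the printed definition and table where the general compliance sentence gives no procedure. It does not depend on what the consent form lists, because the table routes listed and unlisted events alike. It should be corrected, but it does not call the safety data already collected into question.

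**What to change.** In 8.3:

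- Define unexpected as not listed in the consent form in nature or severity. Keep this separate from seriousness, and state what counts as serious, since the section title refers to SAEs but the text gives no definition.
- Put in the immediate column any serious, unexpected event that is at least possibly related to the cell infusion on the 8.2 scale, whatever the care setting.
- Keep fatal and ICU events as their own immediate category, without the unexpected label.
- State how the table and the 312.32 sentence fit together.
- Define life-threatening, so that the 10.2 cross-reference has something to point to. Which events suspend enrollment remains for the sponsor to decide.

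The cost is rewording of the 8.3 definitions and table. Grade and attribution are already recorded, so no new data are needed. The downside is a few more immediate reports.

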9.0 CRITERIA FOR STUDY EVALUATION

- Responses must be maintained with no evidence of AML/MDS for more than four weeks. If chemotherapy continues, there can be no evidence of relapse within four weeks. Response assessments will require a bone marrow aspirate to be performed. In the event of a dry tap or an aspiration that is inadequate for interpretation, a bone marrow biopsy is required for response assessment.
- **Complete Remission (CR):** Complete remission is defined as all of the following:

- Peripheral Blood Counts:
 - Absolute neutrophil count $\geq 1000/\mu\text{L}$
 - Platelet count $\geq 100,000/\mu\text{L}$

- No leukemic blasts in the peripheral blood
 - Adequate erythroid recovery so that RBC transfusions are not necessary
- Bone Marrow:
 - Adequate cellularity
 - No Auer rods
 - < 5% blast cells
- No extramedullary leukemia (such as CNS or soft tissue involvement)

OR

- Complete Response with Incomplete Platelet Recovery (CRp): CRp satisfies all CR criteria except platelets < 100,000/ μ L, but platelet transfusions are not necessary
- **Partial Remission (PR):** Must meet all criteria of a CR except that the bone marrow may contain 5%-24% blasts
- **Treatment Failure:** Failure to achieve a CR (by 60 days after initial induction therapy started)
 - Treatment Failure Due to Resistant Disease:
 - Patients treated appropriately
 - Survived > 30 days after therapy began.
 - Failed to achieve remission due to persistent AML as determined by peripheral blood and bone marrow aspirate and biopsy.
 - Treatment Failure Due to Death of the Patient:
 - Patient died within 30 days of starting protocol therapy.
 - Record whether the patient died with or without evidence of persistent leukemia as determined by peripheral blood and bone marrow aspirate and biopsy.
- **Relapse** - Any of the following, occurring after either CR, CRp, or PR:
 - The reappearance of circulating blast cells not attributable to “overshoot” following recovery from myelosuppressive therapy
 - > 5% blasts in the marrow, not attributable to another cause (e.g., CSF, bone marrow regeneration)
 - Development of extramedullary leukemia

- **Toxicities will be followed using CTCAE criteria.**
Most toxicities will be attributable to the chemotherapy. Toxicity attributed to the cell infusions may include occurrence of GVHD and unexpected duration of myelosuppression. Severity of myelosuppression (hematologic toxicity) will not be taken into account.
- **Time to neutrophil recovery:**
The first of three consecutive days with ANC $>5 \times 10^9/L$.
- **Time to platelet recovery;**
Platelet recovery is reported when the platelet count is $\geq 20 \times 10^9/L$ seven days after platelet transfusion and is maintained for three consecutive lab values obtained on different days.
- **Treatment Related Mortality**
Considered any death that cannot be explained by persistence, relapse or progression of the underlying malignancy once the preparative regimen starts.
- **Acute GVHD**
Acute GVHD will be scored according to the criteria proposed by Przepiorka et al.²⁸
Risk score for acute GVHD will be further assigned based on recent publication by Mac Millan et al.²⁹
Chronic GVHD will be scored according to the consensus criteria.³⁰

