11. CRITERIA FOR REMOVAL OF PATIENTS FROM PROTOCOL THERAPY

11.1 Duration of Treatment

Patients will continue with the therapy specified in this protocol until one of the following occurs:

- Achievement of protocol endpoint CR or CRp after induction and cellular therapy
- Failure to achieve CR or CRp
- Extraordinary Medical Circumstances: If, at any time the constraints of this protocol are detrimental to the patient's health and/or the patient no longer wishes to continue protocol therapy, remove the patient from protocol treatment. In this event.

After removal from protocol therapy, patients will continue to be followed for survival and disease status. Samples for correlative studies will continue to be collected every two months until one year after cell infusion.

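### Section 9 lets a partial remission hold 5%-24% marrow blasts but counts more than 5% after PR as relapse, so an unchanged PR can be scored as a relapse (minor; secondary objective 1.2(e) only)

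*Combined protocol and SAP*

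**What the plan says.** All the definitions at issue are in Section 9.0 of the combined protocol and SAP.

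- **PR:** "Must meet all criteria of a CR except that the bone marrow may contain 5%-24% blasts".
- **Relapse, when it applies:** "Any of the following, occurring after either CR, CRp, or PR".
- **Relapse, marrow criterion:** "> 5% blasts in the marrow, not attributable to another cause". The examples given of another cause are CSF and marrow regeneration. The other two criteria are circulating blasts and extramedullary leukemia, and any one of the three is enough.
- **Maintenance, for all responses:** "Responses must be maintained with no evidence of AML/MDS for more than four weeks".
- **Treatment failure:** "Failure to achieve a CR (by 60 days after initial induction therapy started").

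Section 11.1 names the endpoint that ends protocol therapy: "Achievement of protocol endpoint CR or CRp after induction and cellular therapy". PR is not in it. Secondary objective 1.2(e) covers response rates and response duration and does not say whether PR counts.

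On timing, Section 7.4 says: "A bone marrow examination to document response must be performed in all patients on or before Day 60". The Section 7.1 schedule shows that one marrow after infusion, and its marrow row is empty beyond day 60.

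**The concern.** The PR definition and the relapse rule use overlapping blast ranges. The relapse threshold is a fixed level, not a change from the response marrow, and PR is expressly among the states from which a patient can relapse. A patient can therefore move from PR to relapse with no change in disease.

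Because later marrows are discretionary, two patients with the same stable PR could be scored differently only because one of them had another marrow. A PR with 6%-24% leukemic blasts is also hard to square with the maintenance sentence, which asks for no evidence of disease for more than four weeks. No other section gives PR its own rule for loss of response.

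At stake are the count of PRs, the count of relapses after PR, and any duration of response that includes PR. The May 2020 addendum in Section 10.1 extends the CBU cohort to 60 treated patients in order to settle the question of efficacy, so the response definitions should be usable as written.

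**Working it through.** **Inputs**

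- PR marrow range: 5% to 24% inclusive (Section 9.0).
- Relapse marrow threshold: more than 5%, no rise required, other causes exempt (Section 9.0).
- Mandated marrows after infusion: one, by Day 60 (Sections 7.1 and 7.4).
- Infusion window: at least 24 hours after the last chemotherapy dose and within 72 hours of completing the regimen (Section 5.2).
- Treated patients: 60 CBU, about 20 haplo (Section 10.1).

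The plan gives no figure of its own on this point. Its one precision figure, 13.1 points in Section 10.1, reproduces as 1.96 × √(0.10 × 0.90 / 20) = 0.1315. It concerns complication rates and is not used below.

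**Step 1. Overlap.** Whole-percent values in the PR range: 24 − 5 + 1 = 20. Values above 5%: 24 − 6 + 1 = 19. Share: 19/20 = 95%. Only exactly 5% is a PR that does not meet the relapse threshold. This counts blast values, not patients.

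**Step 2. Scoring of hypothetical patients** (all other PR criteria met, blasts leukemic):

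| Response marrow | Later marrow | Change in disease | Score under Section 9.0 |
|---|---|---|---|
| 15% | 15% | none | PR, then relapse |
| 20% | 10% | improved | PR, then relapse |
| 5% | 5% | none | PR, no relapse |
| 15% | not done | not known | PR, no relapse by the marrow criterion |

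Rows 1 and 2 are mis-scored. Rows 1 and 4 may be the same patient with and without a discretionary marrow.

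**Step 3. Which outcomes are touched.** CR and CRp need less than 5% marrow blasts, so their range does not overlap the relapse region and the CR/CRp rate does not change. The primary safety endpoint and the stopping rules (Sections 10 and 10.2) count grade III-IV GVHD and unexplained prolonged myelosuppression. Neither uses the PR or relapse-after-PR label: a PR requires recovered counts, and the myelosuppression definition already excludes residual leukemia.

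**Step 4. The two 60-day limits (illustration only).** The failure limit runs from the start of induction. The footnotes to the Section 7.1 schedule suggest that Day 60 is counted from infusion. Assume a regimen of L days with the last dose L − 1 days after the first. Infusion then falls between (L − 1) + 1 = L and (L − 1) + 3 = L + 2 days after the start. This gives 5-7 days for L = 5, 7-9 for L = 7 and 10-12 for L = 10. The upper bound is one day later if completion is counted at the end of the last day. With L = 7, Day 60 from infusion is 67-69 days after the start, against a failure limit of 60. Section 5.1 leaves the regimen to the treating physician, so L is an assumption. One CR scored the other way moves the rate by 1/60 = 1.7 points (CBU) or 1/20 = 5.0 points (haplo, as planned).

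**The case against.** The strongest reply is that the plan already treats CR/CRp as the response that matters. Section 11.1 names only those two, Section 9.0 classes failure to reach CR by 60 days as treatment failure, and the maintenance sentence excludes visible disease. A persisting PR is then already a failure, and calling it a relapse changes no specified result. No section specifies an analysis of PR duration.

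Much of this stands, and it keeps the point minor. It does not remove it. Objective 1.2(e) does not exclude PR, and the relapse rule names PR, so Section 9.0 itself expects patients in PR to be followed for relapse. Anyone applying it as written would score rows 1 and 2 of the table wrongly.

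A reader might infer that every stable PR turns into a relapse. The documents do not support that: exactly 5% escapes, blasts with another cause are exempt, and a further marrow must be done.

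A reader might also infer that the two 60-day limits contradict each other, so that CRs found on schedule are recorded as failures. That is not established either. One limit is a latest date for a procedure and the other classifies outcome. A marrow done before both satisfies both, and Section 7.4 advises earlier marrows when counts recover slowly. Day 0 is not defined in the text available for this review, but that text lacks some pages, including the start of the schema, and a definition there cannot be ruled out. Section 3.1 uses the term initial induction therapy for earlier treatment, but reading the failure limit that way is not realistic: a sub-item under the same heading says "Patient died within 30 days of starting protocol therapy".

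**Conclusion.** The definitions are wrong as written, and the consequence is minor. If a further marrow is done, an unchanged or improving PR of 6%-24% meets the relapse rule unless the blasts have another cause. This follows from Section 9.0 alone and needs no outside assumption.

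The effect is limited to a descriptive secondary objective. A reader might infer that the efficacy or safety conclusions as a whole are compromised; Step 3 shows that they are not. That PR is not a success is consistent between Sections 9.0 and 11.1 and is no part of this point. The documents give no number of PRs or of extra marrows, so the size in patients cannot be computed.

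The 60-day limits are a query only. It rests on an inferred Day 0 and an assumed regimen length.

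**What to change.** 1. In Section 9.0, apply the more-than-5% marrow relapse criterion and the sentence requiring no evidence of AML/MDS to CR and CRp only.
2. State that response rate and duration of response are based on CR plus CRp, consistent with Section 11.1, and report PR separately.
3. If PR duration is to be reported, the sponsor should define loss of PR so that an unchanged or falling blast count is not relapse. Blasts above the PR range, circulating blasts or extramedullary disease would be one example; the cut-off is the sponsor's choice.
4. Query: confirm Day 0, and give the failure limit and the response-marrow limit one stated origin, either the start of protocol induction or infusion. If the failure limit changes, report the CR/CRp rate under both limits, because a later limit can only turn failures into CRs.

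The cost is a small wording change and, where needed, re-scoring from marrow results and dates already recorded. No new procedures are needed. The downside is that definitions change partway through the trial. Section 10.2 says more than 30 CBU patients had been enrolled by May 2020, so the change should be dated and disclosed.
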